5.2 Packaging and Labeling

EDP-938- drug product tablets and the corresponding placebo tablets are supplied as tablets and [REDACTED] tablets in [REDACTED]

All the drug product manufacturing, packaging, and release testing are conducted under Current Good Manufacturing Practice regulations. EDP-938- drug products are labeled according to the regulatory guidelines for labeling of investigational products.

5.3 Storage

EDP-938 and placebo tablets will be shipped and stored at the site at [REDACTED]
[REDACTED] Additional information can be found in the in the Pharmacy Manual.

Subjects will be instructed to store study drug in the original bottle at [REDACTED].

5.4 Accountability

Site staff will maintain adequate records of the receipt and disposition of all study drug shipped to and/or procured by the site for this study.

Site and/or pharmacy records (as appropriate for the site) must include dates, bottle numbers, lot numbers, quantities received, quantities dispensed, date and time of administration (Section 5.7), and the identification number of each subject who has received each lot of study drug.

Unused study drug must not be discarded until the end of the study after full drug accountability is performed. Study drug that is dispensed to a subject, but not administered or completely ingested by the subject, must be returned to the pharmacy and the amount remaining recorded in the source documents.

In addition, for drug accountability, subjects should bring study drug (including empty bottles) with them to the study site.

5.5 Handling and Disposal

Study drug must not be used for any purpose other than for administration to subjects enrolled into this clinical study. All study drug bottles that are opened and returned by subjects as well as those that are not opened or assigned to subjects will be retained at the site according to instructions provided by Enanta Pharmaceuticals, Inc. or designees until monitored by the Study Monitor. Full accountability of all study drug distributed to subjects will be documented per Section 5.4.

Enanta Pharmaceuticals, Inc. will provide instructions for the return or destruction of any unused study drug. If Enanta Pharmaceuticals, Inc. authorizes destruction at the study site, the Investigator must ensure that the materials are destroyed in compliance with applicable environmental regulations, institutional policy, and any special instructions provided by Enanta Pharmaceuticals, Inc., and, that the destruction was adequately documented.

5.6 Treatment Assignment/Randomization

Subjects will be randomized to a treatment group using an Interactive Web Response System (IWRS). Subjects will be randomized in a 2:1 ratio to the EDP-938 or placebo treatment group as shown below:

- Treatment Group 1 (approximately 130 subjects): either [REDACTED] (see Section 4.1) of EDP-938 orally QD for 21 days
- Treatment Group 2 (approximately 70 subjects): Placebo orally QD for 21 days

In addition, subject randomization will be stratified based on ribavirin treatment (presence or absence) and ALC (<200 or \geq 200 cells/ μ L) at Screening.

During the Screening Period, subjects will be identified by a unique screening number assigned by the clinical site. Subjects who have completed screening assessments and are eligible for participation in the study will be randomized before the first dose of study drug (Day 1) and assigned a unique four-digit subject number that will be used to identify the subject throughout the study.

5.7 Study Drug Dose and Administration

Complete instructions for dispensing and administering study drug are presented in the study-specific Pharmacy Manual.

Following randomization on Day 1, subjects will receive the first dose of EDP-938 or placebo orally while at the study site. After the first dose, subjects will be instructed to take the study drug orally QD on each of the 20 subsequent days. Subjects will be instructed to take the study drug at approximately the same time every day (\pm 1 hour).

Study site visits should be scheduled close to the time that the subject normally takes the study drug so that dosing can occur at the site. If a visit occurs within 4 hours of the scheduled dosing time, the subject should take the study drug at the site during the visit. If a visit occurs more than 4 hours before or after the scheduled dosing time, the subject should take study drug at the

scheduled time at home. The time and date of doses of study drug taken at the study site should be recorded by site staff in source.

If a subject forgets to take their study drug at the scheduled time, the dose should be taken as soon as the subject remembers; however, the following rules apply:

- No more than one dose should be taken on any calendar day and
- There must be a minimum of 16 hours between doses.

Site staff will record the time and date of all study drug doses taken at the site. Subjects that took study drug at home on the day of a study visit should be asked for the time that dose was self-administered and record it in the electronic case report form (eCRF).

5.7.1 Dispensing of Study Drug

EDP-938 and placebo must be dispensed by a licensed investigational pharmacist or other authorized site staff with appropriate training. Subjects will receive instructions on study drug storage (see Section 5.3) and dosing (see Section 5.7).

5.7.2 Treatment Compliance

Both accountability and study drug compliance will be reviewed at each study site visit as indicated in the SoA (Appendix 1). The number of tablets will be counted, and the site staff will ask the subjects why any doses were missed, if applicable. Any potential reasons for lack of compliance with dosing will be monitored and followed up by the site staff. Compliance assessment may be completed at the study site or by a study site personnel via a home visit.

For any subject considered to demonstrate continued noncompliance of study drug dosing despite continued educational efforts, the Investigator should contact [REDACTED] the Sponsor's Medical Monitor to discuss possible discontinuation of the subject from the study.

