7.2.1 Withdrawal Criteria

Reasons for discontinuation include but are not limited to the following:

- AE
- Lack of efficacy
- Lost to follow-up
- Withdrawal by subject
- Protocol deviation (including noncompliance with study drug or study procedures)
- Pregnancy
- Study terminated by the Sponsor
- Other

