7.2.2 Procedures for Early Discontinuation or Early Termination of Treatment

Subjects who discontinue treatment before completing 21 days of dosing should return to the study site within 24 hours after the last dose of study treatment to complete an EOT visit, including EOT PK sample collection. Subjects should then return to the clinic for the Follow-up Visit 1 (EOT + 1 week) and the EOS visit 4 weeks following the last dose of the study drug.

Subjects who discontinue the study before Day 28 should return to the site within 48 hours to complete Follow-up Visit 1 (EOT + 1 week) procedures. Subjects who discontinue the study early between Day 28 and Day 49 should return to the study site within 48 hours to complete the EOS procedures (see [Appendix 1](#)). Any subject who withdraws with ongoing AEs/SAEs should be followed until resolution of their AE(s) or until the Investigator has determined that the AE(s) has stabilized.

Site staff will attempt to contact any subject who does not return to the site for the EOS visit at least three times using the subject's preferred method of communication, followed by a letter requiring delivery notification if the three attempts were unsuccessful. Any subject who still cannot be reached following those attempts will be considered lost to follow-up. These subjects will be included in the PK and safety analysis as indicated in Section [11.3](#).

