8.3.6 Adverse Events

The Investigator is responsible for the detection and documentation of events meeting the criteria and definition of an AE or SAE as provided in Section 9.1 of this protocol. All AEs and SAEs must be recorded in the source documents and eCRF as described in Section 9.2. At all study site visits, the Investigator or designee should inquire about the occurrence of AEs. The following are examples of open-ended questions that may be used to obtain this information: “How are you feeling?”; “Have you had any medical problems recently?”; and “Have you taken any new medicines since your last visit/assessment?”

It is the Investigator’s responsibility to ensure any necessary additional therapeutic measures and follow-up procedures are performed and documented in the subject source notes and eCRF.

8.3.7 Lower Respiratory Tract Complications Clinical Source for Endpoint Adjudication Committee Review

During the course of the study, it is anticipated that chest images, and other clinical evaluations and laboratory tests will be performed as part of standard of care if there is any concern of a LRTCs. In addition to eCRF data relevant to safety assessments, the following source will be submitted to adjudicators:

- Chest images: Images and results for chest imaging used for Screening and eligibility, including the comparison chest imaging, and all scans done as part of the standard of care while subjects are on study, will be collected and stored electronically for review by the Endpoint Adjudication Committee.
- Results of all local microbiological tests performed while on study (all bacterial, viral, fungal, parasitic, or other test results from samples obtained from any respiratory specimen [eg, bronchoalveolar lavage, sputum, pleural fluid, lung tissue] and from blood specimens, including bacterial culture, viral polymerase chain reaction, and serology studies).
- Clinical notes with range of dates, including outpatient notes with vital signs, outpatient laboratory and hospital discharge summaries, as appropriate.
- Autopsy reports (if performed).
- Other supporting documentation, as requested, including by the Endpoint Adjudication Committee.

8.3.8 [REDACTED]

[REDACTED]

[REDACTED]

[REDACTED]

[REDACTED]

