5.1 Disposition

A summary of the analysis populations includes the number and percentage of subjects in each analysis population (ITT, mITT by RT-qPCR, mITT by CBIA, SAF, and PK) by treatment group and overall. The number and percentage of subjects excluded from each analysis population and the reasons for exclusion will also be presented. All percentages will be based on the number of subjects randomized.

Subject disposition will be summarized by treatment group and overall for all subjects who provided informed consent. A disposition of subjects includes the number and percentage of subjects for the following categories: subjects who were randomized, subjects who completed study treatment, subjects who discontinued study treatment, subjects who completed the study, subjects who discontinued from the study. All percentages will be based on the number of subjects randomized. The reasons for discontinuation of study treatment and study participation will also be summarized in this table.

The reason for discontinuation of study treatment or study participation may include any of the following: adverse event, lack of efficacy, lost to follow-up, pregnancy, protocol deviation, study terminated by sponsor, withdrawal by subject, physician decision, COVID-19, or other reason.

Subject disposition data and exclusions from analysis populations will also be presented in a listing.

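### The protocol lets non-compliance, and the SAP lets lack of efficacy or protocol deviation, end study participation; LRTC observation may then stop before Day 28 and the subject be scored event-free

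*Protocol*

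**What the plan says.** **Leaving the study for non-compliance.** Protocol 5.7.2 covers subjects who keep missing doses despite education. The investigator contacts the medical monitor "to discuss possible discontinuation of the subject from the study".

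**Reasons.** Protocol 7.2.1, headed as withdrawal criteria, gives one open-ended list. It includes "Lack of efficacy" and "Protocol deviation (including noncompliance with study drug or study procedures", and does not say which entries end treatment and which end participation. SAP 5.1 uses one list for both: "The reason for discontinuation of study treatment or study participation may include any of the following: adverse event, lack of efficacy". Protocol deviation appears later in that list.

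**Consequences.** Protocol 7.2.2 separates the two paths. For those who only stop drug: "Subjects should then return to the clinic for the Follow-up Visit 1 (EOT + 1 week) and the EOS visit 4 weeks following the last dose". For those who leave: "Subjects who discontinue the study before Day 28 should return to the site within 48 hours to complete Follow-up Visit 1". The same section keeps following ongoing AEs and SAEs after withdrawal until they resolve or stabilize.

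**Endpoint data.** The primary endpoint is adjudicated LRTC through Day 28. Protocol 8.3.7 sends the adjudicators "all scans done as part of the standard of care while subjects are on study" and "Results of all local microbiological tests performed while on study". Every LRTC category in Protocol 8.8 needs new chest-imaging findings.

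**Missing data.** Protocol 11.6.1 treats missing LRTC as a nonresponse, without saying what that means for an adverse endpoint. SAP 8.1.1 counts it as no LRTC. Protocol 7.2 says withdrawn subjects are not replaced.

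**The concern.** Non-compliance and lack of efficacy may be grounds for reconsidering treatment, but neither is a reason to stop observing a consenting subject. Both can be related to the outcome or to the drug. A subject recorded as leaving for lack of efficacy is presumably doing badly, and missed doses may reflect poor tolerability. If such a subject leaves the study, an LRTC that appears later but before Day 28 may never reach adjudication, and the SAP then counts the subject as event-free.

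If the drug works, lack-of-efficacy exits could fall mainly on placebo and hide a real difference. If tolerability drives missed doses, non-compliance exits could fall mainly on active and make the drug look protective. Respiratory failure or death through Day 49, a secondary endpoint in the protocol, is exposed to the same loss.

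**Working it through.** **1. The two paths compared**

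| | Stops drug only | Leaves study before Day 28 |
|---|---|---|
| Visits (7.2.2) | EOT, EOT + 1 week, last dose + 4 weeks | One visit within 48 hours |
| Afterwards | End of study | Only follow-up of ongoing AEs/SAEs |
| Images and microbiology to adjudicators (8.3.7) | Collected while on study | No stated collection after exit |

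A subject who stops drug on Day d has the final visit at about Day d + 28. The earliest case is Day 1 + 28 = Day 29, so Day 28 is always covered. Day 49 is reached only if d = 21. Protocol 7.2 bars further data collection only when consent for future information is also withdrawn. For other exits collection is not forbidden, but no section provides for it.

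**2. Inputs from Protocol 11.2**

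These are 30% LRTC on placebo, a 20% reduction, 90% power, two-sided alpha 0.05, unpooled z-test, 2:1 allocation, about 160 subjects, 15% dropout and 190 randomized. I read the reduction as 20 points (30% to 10%), because a relative 20% reduction (30% to 24%) would need about 2,640.

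The plan's 160 does not reproduce:

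- n(placebo) = (1.960 + 1.282)² × [0.30 × 0.70 + 0.10 × 0.90 / 2] / 0.20² = 67, so the total is 67 + 134 = 201.
- Allocation 1:1 would give 158.
- The dropout step is consistent: 160 / 0.85 = 188.2, rounded up to 189, against 190 stated.

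The sample-size discrepancy is a separate matter and this point does not depend on it. Below I take 190 randomized as 63 placebo and 127 active.

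**3. Loss on placebo only, missing counted as no LRTC**

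Assume a share s of placebo subjects heading for LRTC exit first, and none on active. The shares are assumptions; the documents give no exit rates by arm.

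- Observed placebo rate = 30% × (1 − s).
- Power = Φ(difference / SE − 1.960), with SE = √[p₁(1 − p₁)/63 + 0.10 × 0.90/127].

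| s | Placebo | Active | Difference | SE | Power |
|---|---|---|---|---|---|
| 0 | 30% | 10% | 20 points | 0.0636 | 88% |
| 10% | 27% | 10% | 17 points | 0.0619 | 78% |
| 20% | 24% | 10% | 14 points | 0.0600 | 65% |

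**4. Dependence on the missing-data rule**

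Per 100 placebo subjects, 30 are heading for LRTC and 3 or 6 exit.

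- Exits excluded: 27/97 = 27.8% or 24/94 = 25.5%, so differences of 17.8 or 15.5 points.
- Exits counted as LRTC: (27 + 3)/100 or (24 + 6)/100, both 30%. This loss then disappears, but any exit not heading for LRTC would be counted against its arm.

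**5. Loss on active only, no true effect**

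Assume 30% in both arms and 15% of active subjects exiting. The 15% borrows the plan's dropout figure; placing it all on active is an assumption. Observed active rate = 30% − 15% × (LRTC risk among those exiting).

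| Risk among exits | Placebo | Active | Chance of a false claim for active (nominal 2.5%) |
|---|---|---|---|
| 30% | 30% | 25.5% | 9.5% |
| 60% | 30% | 21% | 26% |
| 100% | 30% | 15% | 62% |

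The last row is an extreme bound.

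**The case against.** The case on the other side has real force on several points.

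- **Removal is permitted, not required.** Section 5.7.2 calls for a discussion of a possibility. A reader might infer that the protocol directs non-compliant subjects out of the study; it does not.
- **The lists mainly record disposition.** Section 7.2.1 includes loss to follow-up and other, and SAP 5.1 describes a reporting table. Neither instructs anyone to withdraw a subject. SAP 5.1 names protocol deviation, not non-compliance; the link comes from the wording in 7.2.1. Still, both accept these reasons for a study exit, and nothing tells a site otherwise.
- **Exit does not end all contact.** Ongoing AEs and SAEs are followed, and Protocol 9.2.1 counts progression of underlying disease as an AE, so a worsening subject would often still be followed clinically. That follow-up tracks a known event to resolution or stability; it does not provide for ascertaining and adjudicating LRTC through Day 28. Section 8.3.7 lets adjudicators request other supporting documents, which might recover some cases but is not systematic.
- **The exit visit is not uniquely deficient.** It has no chest imaging, but no visit after Screening schedules any; on-study imaging comes from standard of care. What exit ends is the stated collection of that imaging.
- **Added treatment need not mean exit.** Ribavirin is allowed (4.2.1), and where a newly needed azole conflicts with study drug, 5.8 speaks of discontinuing dosing. No section ties other treatment to withdrawal for lack of efficacy.
- **Imbalance between arms is inferred.** The documents contain nothing on exit rates by arm.

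**Conclusion.** The point holds as a gap in the plan for observation. The documents leave open a study exit for reasons that can be related to outcome or tolerability, provide no endpoint collection after it, and score the missing result as event-free.

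Its size is not known. Under assumed placebo-only losses of 10% to 20% of would-be LRTC cases, the planned 20-point difference is observed as 17 to 14 points and power at 190 falls from 88% to between 78% and 65%. These figures rest on the SAP's missing-equals-no-event rule and on no loss on active. Losses on active bias the other way. A reader might infer a known bias toward no effect, or that such exits occurred; the documents support neither.

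The effect on the present report is small. The study ended with 9 randomized, SAP 12 drops between-arm tests and intervals, and it deletes the respiratory failure or death endpoint. The one place it could show is the descriptive LRTC proportion: if the split were 6 and 3 (assumed from 2:1), one exit would move it by up to 1/6 (17 points) or 1/3 (33 points).

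**What to change.** For any protocol that reuses this text:

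- Reconcile Protocol 5.7.2, 7.2.1 and 7.2.2 and SAP 5.1 so that non-compliance, lack of efficacy and protocol deviation are not reasons to end study participation.
- State that all randomized subjects, on or off drug, stay in follow-up for LRTC through Day 28 and for respiratory failure and death through Day 49, counted from first dose, unless consent is withdrawn. Counting from first dose matters because visits timed from an early last dose end before Day 49.
- Have 8.3.7 collect images and microbiology over that whole period.

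The change concerns observation only. Whether study drug is stopped stays with the investigator and medical monitor.

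For the present report, list each study exit with its reason, study day and last available LRTC information, so that a reader can see which subjects were counted as event-free without full observation to Day 28.

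The cost is protocol and SAP wording, changes to the eCRF reason lists, and a few extra follow-up contacts. The report needs one listing.

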5.8 Prohibited Medications

Following drugs, including over-the-counter medications and supplements with equivalent efficacy, will be prohibited before the study and from the first dose of study drug on Day 1 through Day 49 or early termination:

- Use of or intention to use any medication or supplement known to be a moderate or strong inducer or inhibitor of the [REDACTED] enzyme within 14 days before signing the ICF and throughout the study, with the exception of prophylactic azole antifungal therapies (e.g., fluconazole, itraconazole, ketoconazole, isavuconazole, posaconazole, and voriconazole), which are permitted with EDP-938 dose adjustment (Section 4.2.2).
- Treatment with azole antifungals that are weak inhibitors of [REDACTED] (e.g., clotrimazole) is allowed without EDP-938 dose adjustment.

- For HCT recipients on prophylactic antifungal therapy with azole antifungals, treatment with additional moderate or strong inhibitors of [REDACTED] outside the azole antifungal class is exclusionary within 14 days of signing the ICF and throughout the duration of the study.
- For subjects not on prophylactic antifungal therapy with azole antifungals at screening, initiation of new azole antifungals that are moderate or strong inhibitors of [REDACTED] is prohibited. If treatment with these agents is considered medically necessary after Day 1, dosing with EDP-938 should be discontinued.
- A comprehensive list of [REDACTED] inducers and inhibitors can be found at:
<https://www.fda.gov/drugs/drug-interactions-labeling/drug-development-and-drug-interactions-table-substrates-inhibitors-and-inducers>.
- Cyclosporine, a moderate [REDACTED] inhibitor, has been shown in a Phase 1 DDI study (EDP 938-002) evaluating the effect of cyclosporine on EDP-938 levels to have no apparent effect on the EDP-938 peak exposure and a weak effect on EDP-938 systemic exposures [REDACTED]. In the same study, (EDP -938-002) coadministration with prednisone, a weak [REDACTED] inducer, showed no apparent effect on EDP-938 exposure. Based on these results, no dose adjustments of EDP-938 when it is coadministered with cyclosporine or prednisone will be necessary.
- Use of nonmarketed (according to region) or investigational agents, vaccines, biological products within 30 days or five half-lives before signing the ICF, whichever is longer, and throughout the study.
- Use of any investigational monoclonal anti-RSV antibodies within 4 months or five half-lives of signing the ICF, whichever is longer, or use of any investigational RSV vaccines after HCT, and throughout the study.

6. BLINDING

6.1 Maintaining the Blind

The study will be double-blinded, meaning that the subjects, investigators, and site staff will be blinded to treatment assignment until the completion of the study. All site staff will be blinded to treatment assignment except for the following individuals:

- Unblinded Enanta/ [REDACTED] statistician for purpose of generating and monitoring the randomization list
- Unblinded Enanta representatives not associated with the day-to-day conduct of the study as outlined in a separate DMC charter
- Unblinded members of the DMC for purposes of unblinded data review
- Unblinded Drug Supply Chain personnel for the purpose of monitoring drug supplies
- Enanta, [REDACTED], and Regulatory Affairs representatives when required to satisfy regulatory reporting requirements
- Bioanalytical laboratory for the purpose of measuring drug concentrations

During the study, investigators, site personnel, and blinded contract research organization/Sponsor staff will not have access to results for individual subjects that could impact clinician assessments, including results for RSV viral load, confirmatory respiratory pathogen panel testing, biomarkers, and PK.

